Adverse event seriousness, severity grade, and relationship to study treatment will be assessed by the investigator. Severity grade will be defined by the National Cancer Institute (NCI) Common Terminology Criteria for Adverse Events (CTCAE) version 4.0.

TUMOR ASSESSMENTS

Tumors will be assessed with radiographic studies at baseline and every two months through week 52, and then every 12 weeks:

For patients with measurable visceral metastases CT scans with contrast or MRI are required. Measurable disease is defined as at least one lesion that can be accurately measured in at least one dimension (longest diameter to be recorded). Each lesion must be greater than or equal to 10 mm when measured by CT, MRI or caliper measurement by clinical exam; or greater than or equal to 20 mm when measured by chest x-ray. Lymph nodes must be greater than or equal to 15 mm in short axis when measured by CT or MRI.

For patients with only bone metastases (Exploratory branch) FDG-PET/CT scan is the only radiographic test required for follow-up. FDG-PET/CT assessment will include standard assessment of SUV_{max}, as well as advanced volumetric measures including SUV_{peak}, metabolic tumor volume (MTV), and total lesion glycolysis (TLG)

PHARMACOKINETIC ASSESSMENTS

None.

BIOMARKER ASSESSMENTS

All patients included in this study will have baseline measurements of resting plasma metanephrines and chromogranin A. Approximately 60% of patients with malignant pheochromocytomas and paragangliomas experience an excessive secretion of catecholamines. In patients with an excessive production of metanephrines at baseline, plasma metanephrines will be obtained every two months. Chromogranin A will be measured at baseline and every two months in all patients. We will correlate biomarkers with overall prognosis, symptoms, and responsiveness to cabozantinib.

Translational Research

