A recently published retrospective intention-to-treat study described potential clinical benefits derived from sunitinib in patients with metastatic PHs and PGs⁷. Seventeen patients with progressive disease over a period of 6 months were treated with 37.5-50 mg of sunitinib daily, 4 weeks on, 2 weeks off. Patients were followed with radiographic and biochemical studies every 2 to 3 months. As per RECIST 1.1, 8 patients (47%) exhibited clinical benefits: 3 patients had partial responses and 5 had prolonged stabilization of disease, including 4 patients with extensive skeletal metastases (but not other metastases) identified by18F-FDG-PET/CT scan. The tumors that responded to treatment also exhibited more than 30% reduction in glucose uptake 2-3 months after initiation of treatment compared with baseline. Patients who experienced partial response or prolonged stabilization of disease improved blood pressure and some discontinued treatment with antihypertensive medications. Most patients who benefited from sunitinib carried SDHB mutations. Unfortunately, most patients who experienced clinical benefits, later developed tumor progression⁷.

Hypothesis

Development of tumor progression and resistance to sunitinib may be related to the compensatory activation of molecular pathways that are not inhibited by this drug, such as the c-MET receptor pathway. MET and VEGFRs cooperate to promote tumor angiogenesis and MET upregulation may occur as a response to the VEGFs pathway inhibition leading to tumor resistance and growth8. MET activation is a common feature of human tumors and it is frequently observed in patients with bone metastases⁸. Molecular analyses of malignant PHs and PGs from a few patients participant of phase one clinical trials have found c-MET receptor gene mutations (unpublished data). Cabozantinib is a tyrosine kinase inhibitor with antiangiogenic and antitumor activity that targets the VEGF, c-MET, and RET receptors. This drug has been recently approved for the treatment of progressive metastatic medullary thyroid carcinoma another neuroendocrine tumor⁹. Of interest, cabozantinib has also shown effectiveness in patients with castration resistant prostate, breast, and renal cell carcinomas metastatic to the skeleton^{10, 11, 12}. Therefore, simultaneous inhibition of MET and VEGFRs by cabozantinib may provide a broad spectrum of antineoplastic activity and prevent tumor resistance in patients with malignant PHs and PGs.

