1.2.3.2.1 Adverse Events

Adverse Events in Subjects with Solid Tumors Treated with Cabozantinib as Single Agent (Pooled Single-Agent, Open-Label Studies)

The most frequently (≥ 20%) observed AEs in 1311 patients participant in single agent studies as of February 28, 2013 regardless of causality, were fatigue: (66.7%), diarrhea (63.1%), decreased appetite (51.9%), nausea (51.9%), weight decreased (36.0%), PPES (35.9%), vomiting (34.1%), constipation (33.2%), dysgeusia (28.0%), hypertension (27.8%), dysphonia (26.3%), abdominal pain (23.3%), aspartate aminotransferase (AST) increased (23.0%), dysphonia (21.3%), headache (20.9%), rash (20.4%), and ALT increased (20.2%). The safety profile of single-agent cabozantinib is consistent across tumor types (Investigator Brochure, version 9, 2013).

The most frequently ($\geq 20\%$) observed AEs reported as related to cabozantinib, were fatigue (60.0%), diarrhea (56.1%), decreased appetite (44.1%), nausea (42.4%), PPES

(35.6%), weight decreased (29.1%), dysgeusia (27.1%), hypertension (24.0%), vomiting (23.5%), dysphonia (22.0%), and AST increased (20.1%).

The most common AEs (\geq 5%) reported at severity of Grade 3 and above include fatigue (15.9%), diarrhea (11.1%), hypertension (9.7%), PPES (8.9%), lipase increased (6.8%), PE (5.9%), abdominal pain (5.5%), decreased appetite (5.3%), and asthenia (5.0%)(Investigator Brochure, version 9, 2013).

Adverse Events in Subjects with MTC Treated with Cabozantinib as Single Agent Compared with Placebo (XL184-301)

The cut-off date for AE data comparing the two treatment arms, cabozantinib versus placebo, in Study XL184-301 was 28 February 2013 (Investigator Brochure, Version 9, 2013). The most frequent AEs (\geq 30% incidence) in cabozantinib-treated subjects were diarrhea (69.6% in cabozantinib-treated subjects vs 35.8% in placebo-treated subjects), weight decreased (55.6% vs 11%), palmar-plantar erythrodysesthesia syndrome (52.3% vs 1.8%), decreased appetite (48.6% vs 15.6%), nausea (45.8% vs 21.1%), fatigue (41.6% vs 30.3%), dysgeusia (34.6% vs 5.5%), hair color changes (33.6% vs 0.9%), and hypertension (30.8% vs 4.6%).

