2 STUDY OBJECTIVES AND DESIGN

2.1 Study Objectives

The objectives of this study are as follows:

Primary Endpoint (14 patients with measurable disease)

To estimate best overall response rate by RECIST 1.1¹³ in patients with measurable disease determined by a. CT or b. MRI

Secondary Endpoints (All patients)

- 1. To estimate progression-free survival at 1-year
- 2. To correlate blood pressure control and change/discontinuation of antihypertensive medications with tumor responses
- 3. To correlate symptomatology evaluation by the MD Anderson symptom Inventory (MDASI) with tumor responses
- 4. To correlate plasma metanephrines and chromogranin A with tumor responses
- 5. To correlate plasma C-reactive protein and interleukin-6 with symptoms and tumor responses
- 6. Toxicity assessment by the Common Terminology Criteria for Adverse Events (CTCAE)
- 7. To correlate both c-MET expression by IHC as well as MET amplification by FISH in archived samples and correlate these biomarkers with overall prognosis and responsiveness to cabozantinib.

Exploratory Endpoints (For patients with only bone metastases)

- 1. Best overall response rate in patients with bone metastases only (8 patients) as determined by FDG-PET/CT
- 2. FDG-PET/CT SUV_{max}, advanced volumetric measures including SUV_{peak}, metabolic tumor volume (MTV), and total lesion glycolysis (TLG)
- 3. Time to skeletal related events
- 4. Incidence of skeletal related events at 4 months and one year
- 5. Markers of bone turnover (bone specific alkaline phosphatase and CTx)

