5.3 Post-Treatment Period

Subjects will return to the study site 30 to 37 days after their last dose of cabozantinib to complete end-of-study assessments.

Laboratory and physical examinations will be performed. Remaining study treatment will be returned by the subject, and treatment compliance will be documented. Additional follow-up will occur for subjects with AEs related to study treatment that are ongoing at the time of this visit, and for subjects with SAEs related to study treatment that occur after the time of this visit.

²Every 4 weeks through Week 24, then every 8 weeks through 52 weeks, then every 12 weeks.

³All sites of known disease must be assessed. To occur every 8 weeks during the first 52 weeks, then every 12 weeks.

⁴Patients with both bone and visceral metastases.

⁵Patients with bone metastases only. This is the **only tumor assessment for patients with bone metastases only**.

⁶ No additional measurements of plasma metanephrines are needed in patients with normal plasma metanephrines at baseline (Non-functioning PH or PG).

⁷ Starting after week 24, nursing phone calls to take place every 8 weeks, at the 4 week period between visits (+/- 5 days). After week 52, phone calls to take place every 12 weeks, at the 6 week period between visits (+/- 5 days). Phone calls will comprise AE and concomitant medication assessments.

⁸ MDASI questionnaires will be completed if the patient can be contacted and is willing and able to complete the questionnaire. While patients are encouraged to complete questionnaires at all scheduled time points, patients may refuse to complete a questionnaire at any time.

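### Bone-only branch: FDG-PET uptake is read without any stated correction for weight change, so weight loss on cabozantinib can bias SUV and TLG downward

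*Combined protocol and SAP*

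**What the plan says.** The first exploratory endpoint in Section 2.1 is "Best overall response rate in patients with bone metastases only (8 patients) as determined by FDG-PET/CT". The second lists SUVmax and SUVpeak with "metabolic tumor volume (MTV), and total lesion glycolysis (TLG"). The Tumor Assessments part of the synopsis and item 2 of Section 5.1 both state: "FDG-PET/CT assessment will include standard assessment of" SUVmax, followed by the same volumetric measures. Footnote 5 of Table 5-1 makes this scan the "only tumor assessment for patients with bone metastases only".

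No section says whether SUV is scaled to body weight or to lean body mass, and none sets a PET cut-off for response or progression. Section 5.5 asks for the same assessment method each time. The only numeric PET change in the documents is in Section 1.1, where tumors that responded to sunitinib showed "more than 30% reduction in glucose uptake 2-3 months after initiation of treatment compared with baseline".

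On weight, Section 1.2.3.2.1 reports "weight decreased (55.6% vs 11" (per cent, cabozantinib against placebo) in the medullary thyroid cancer trial. In the pooled 1311 single-agent subjects it reports 36.0% regardless of cause and 29.1% judged related. Sections 3.3.1.3 and 3.3.1.5 expect weight loss in this trial too. Table 5-1 collects height at screening and weight at the scheduled visits.

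The first secondary endpoint, "To estimate progression-free survival at 1-year", covers all patients, so its imaging component in this branch also comes from PET.

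**The concern.** Body-weight SUV is lesion activity concentration multiplied by body weight and divided by injected activity. If a patient loses mainly fat, which takes up little FDG, the lesion may take up the same share of the injected activity as before, yet SUV falls because weight has fallen. TLG is built on SUV and falls with it. MTV is a volume and is affected only if its boundary is drawn at a fixed SUV cut-off.

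Repeating the same method at every visit does not prevent this, because body-weight SUV itself drifts with weight. The drift points toward apparent benefit, is linked to a known effect of the drug, and occurs in a single-arm study with no other tumor imaging in this branch. At stake are exploratory endpoints 1 and 2 and the PET-read part of progression-free survival in these patients.

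**Working it through.** **Inputs from the documents.** Branch size 8 (Section 2.1). Weight-decreased incidence 29.1%, 36.0% and 55.6% (Section 1.2.3.2.1). Background PET figure 30% (Section 1.1). Planning rate 45% (Section 7).

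**Assumptions not in the documents.** SUV is normalised to body weight. The amount of weight lost is unknown, so 5%, 10% and 20% are shown. The split of the loss between fat and lean mass is unknown, so a range is shown.

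**1. The plan's own figure.** 0.45 ± 1.96 × √(0.45 × 0.55 / 8) = 0.45 ± 0.345, which is 10.5 to 79.5%. This reproduces the stated interval. It does not depend on how SUV is measured.

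**2. How many of the 8 might be affected.** 8 × 0.291 = 2.3; 8 × 0.360 = 2.9; 8 × 0.556 = 4.4. The chance of at least one, 1 − (1 − p)^8, is 0.94, 0.97 and above 0.99. These counts carry over rates from other doses and tumor types.

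**3. Size of the bias.**
- Upper bound: all lost mass is fat and lesion uptake per injected activity is unchanged. The SUV ratio is then 1 − loss, so losses of 5, 10 and 20% lower SUV by 5, 10 and 20%.
- Mixed loss: assume 80 kg with 60 kg lean mass, and uptake that rises as lean mass falls, so SUV is proportional to weight ÷ lean mass. For a 10% loss (8 kg):
  - 75% fat: (72/58) ÷ (80/60) = 0.931, a fall of 6.9%.
  - 50% fat: (72/56) ÷ (80/60) = 0.964, a fall of 3.6%.
  - 25% fat, which is proportional loss: (72/54) ÷ (80/60) = 1, no change.
- If lesion uptake per injected activity rises fully to compensate, the effect is also zero.

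**4. What this does near a boundary (upper bound).** The true fall that reads as 30% is 1 − 0.70/(1 − loss): 26.3%, 22.2% and 12.5% for losses of 5, 10 and 20%. With no true change, a reading of −30% needs a 30% weight loss. In the other direction, a true 30% rise with a 10% loss reads as 1.30 × 0.90 = 1.17, a rise of 17%.

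**5. Effect on the branch rate.** One reclassified patient is 1/8 = 12.5 points, for example from 3/8 = 37.5% (exact 95% CI 8.5 to 75.5%) to 4/8 = 50% (15.7 to 84.3%).

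**6. What a correction removes.** Dividing out true lean mass would remove the bias in both cases of step 3 where it arises. In practice lean mass is predicted from height and weight, and the prediction counts part of a pure fat loss as lean. With a standard formula and illustrative sizes (man 85 kg, 175 cm; woman 70 kg, 163 cm), a 10% pure fat loss still lowers the lean-normalised value by 5.5% and 6.0%. A lesion-to-blood-pool ratio from the same images has no weight term, because weight and injected activity appear in numerator and denominator and cancel.

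**The case against.** A reader might infer that weight loss alone can pass for a metabolic response. The documents do not support that. By step 4 it would take a 30% weight loss to reach a 30% fall. The documents give how often weight fell, not by how much, and weight decreased is absent from the list of Grade 3 or higher events at 5% or more. The 30% is also a remark on a sunitinib series and not a response rule for this trial.

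A reader might also carry 55.6% straight into this trial. That figure comes from 140 mg daily with median exposure of 315 days against 104 on placebo (Sections 1.2.3.1 and 1.2.3.2), while this trial starts at 60 mg (Section 3.2). It is also not restricted to related events. The pooled 29.1 to 36.0% is the fairer range, though it too mixes doses.

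Further objections have force. Body-weight SUV is assumed. Section 7 counts stable disease as response under RECIST without saying whether PET follows; if it does, a move from stable disease to partial response leaves the rate unchanged. Weight is recorded, so a correction could be computed afterwards, and the branch has non-PET endpoints such as "Time to skeletal related events" and bone-turnover markers. The branch is exploratory and its interval is already very wide.

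These points limit the size and importance of the issue but do not remove it. If stable disease counts, the bias acts through masked progression instead. Recorded weight helps only if the analysis uses it, and none of the other endpoints measures lesion uptake.

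**Conclusion.** The point holds as a modest measurement bias that is cheap to correct. If SUV is scaled to body weight, weight loss can lower SUV and TLG by between zero and the percentage lost; a 10% loss gives 0 to 10%, depending on how much is fat and whether uptake compensates. At the pooled rates, two or three of the eight patients might have a weight-decreased event. The bias can exaggerate the reported SUV and TLG changes, tip a borderline response or hide progression.

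How often a call would change cannot be worked out or ruled out, because no PET cut-off is set and the size of weight loss is not given. The effect is confined to the exploratory PET endpoints and the PET-read part of progression-free survival in this branch. The primary endpoint, RECIST on CT or MRI, is untouched.

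**What to change.** In the Tumor Assessments synopsis, Section 5.1 item 2 and exploratory endpoint 2:

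- Report SUVmax, SUVpeak and TLG normalised to lean body mass, using weight on the day of the scan and the height in Table 5-1, alongside the body-weight values.
- Add the lesion-to-blood-pool ratio from the same images as a pre-specified sensitivity check, since formula-based lean-mass normalisation removes only part of the bias.
- State for each patient whether the FDG-PET response or progression call differs between the measures.

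The cost is a sentence or two of protocol text, one extra region drawn on scans already planned, and a little more analysis. No new scan is needed; the weight must be taken on the scan day. Lean-mass values are less directly comparable with series that report body-weight SUV, which is why both should be shown. If the imaging group already uses lean-mass normalisation, stating so settles the main part of the point.

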1.2.3.2.2 Serious Adverse Events

Serious Adverse Events in Subjects with Solid Tumors Treated with Cabozantinib as Single Agent (Pooled Single-Agent, Open-Label Studies)

The most commonly reported SAEs (\geq 2%) were pulmonary embolism (5.1%), vomiting (3.4%), dehydration (3.2%), pneumonia (3.0%), nausea (3.0%), abdominal pain (2.4%), diarrhea (2.4%), deep vein thrombosis (DVT; 2.1%), and convulsion (2.0%)(Investigator Brochure, version 9, 2013).

Serious Adverse Events in Subjects with MTC Treated with Cabozantinib as Single Agent Compared with Placebo (XL184-301)

The most commonly reported SAEs ($\geq 2\%$) occurring on the cabozantinib-treatment arm of Study XL184-301 were pneumonia (4.2%), pulmonary embolism (3.3%), mucosal

inflammation (2.8%), hypocalcemia (2.8%), dysphagia (2.3%), and dehydration (2.3%)(Investigator Brochure, version 9, 2013).

1.2.3.2.3 Deaths

As of 28 February 2013, 192 fatal SAEs were reported (182 on single-agent cabozantinib or cabozantinib in combination with other therapies, 10 on placebo) across all open-label or unblinded company-sponsored studies (Studies evaluated include XL184-001, XL184-002, XL184-008, XL184-014, XL184-201, XL184-202, XL184-203, XL184-205, XL184-209, XL184-900, and all clinical pharmacology studies (n=1754). The majority of these SAEs were attributed to disease progression (70.3%) (Investigator Brochure, Version 9, 2013).

Fifty-seven subjects had fatal SAEs that were attributed to reasons other than PD. 53 subjects received cabozantinib and four received placebo. Of the 53 cabozantinib-treated subjects, 27 had events assessed as related to cabozantinib study treatment (24 as a single agent, 3 in combination with erlotinib) and 26 subjects had events attributed to reasons other than PD or study treatment (20 as a single agent, 6 in combination with other therapies). Fatal side effects not attributed to disease progression for Cabozantinib-treated subjects on open-label or unblinded studies include single cases of GI hemorrhage, hemoptysis, PE, intestinal perforation, enterocutaneous fistula, diverticular perforation, and peritonitis, 3 patients who had intracranial hemorrhage, and 4 cases who died of respiratory failure (Investigator Brochure, Version 9, 2013).

1.1.1.4 Clinical Pharmacokinetics

Population PK analysis of cabozantinib was performed using data collected from 289 cabozantinib-treated subjects from XL184-301, XL184-001, and XL184-201 with solid tumors including MTC following oral administration of 140 mg daily doses. The predicted effective half-life is approximately 55 hours, V/F is approximately 349 L, and CL/F at steady-state is estimated to be 4.4 L/h. The terminal half-life (for predicting drug

washout) is approximately 120 hours. Following oral administration of cabozantinib, Tmax ranged from 2 to 5 hours post-dose. Repeat daily dosing of cabozantinib at 140 mg for 19 days resulted in 4- to 5-fold mean cabozantinib accumulation (based on AUC) compared with a single dose administration; steady state was achieved by Day 15. Cabozantinib is highly protein bound in human plasma (\geq 99.7%) (Investigator Brochure, Version 9, 2013).

The PK evaluation of cabozantinib in the pediatric population is ongoing. A population PK analysis did not identify clinically relevant differences in clearance of cabozantinib between females and males or between Whites (89%) and non-Whites (11% [<4% were Asian]). Cabozantinib PK was not affected by age (20-86 years).

Within a 48-day collection period after a single dose of 14C-cabozantinib in healthy subjects, approximately 81% of the total administered radioactivity was recovered with 54% in feces and 27% in urine. A PK study of cabozantinib in patients with renal impairment (XL184-017) is ongoing. The results of a population PK analysis suggested that mild to moderate renal impairment (creatinine clearance value ≥30 mL/min) does not have a clinically relevant effect on the clearance of cabozantinib. The PK evaluation of cabozantinib in subjects with hepatic impairment (XL184-003) is ongoing; preliminary data suggest that subjects with mild hepatic function impairment (Child-Pugh A) show a 59% higher plasma AUC0-∞ for cabozantinib as compared with matched healthy subjects. A high-fat meal increased Cmax and AUC values by 41% and 57%, respectively relative to fasted conditions in healthy subjects administered a single 140 mg oral cabozantinib dose (Investigator Brochure, Version 9, 2013).

Cabozantinib is a substrate of CYP3A4 in vitro. Inhibition of CYP3A4 reduced the formation of the cabozantinib N-oxide metabolite by >80%. Inhibition of CYP2C9 had a minimal effect on cabozantinib metabolite formation (i.e., a <20% reduction). Inhibition of CYP1A2, CYP2A6, CYP2B6, CYP2C8, CYP2C19, CYP2D6 and CYP2E1 had no effect on cabozantinib metabolite formation. Cabozantinib AUC was increased 38% with coadministration of the strong CYP3A4 inhibitor ketoconazole and decreased 77% with coadministration of the strong CYP3A4 inducer rifampin (Investigator Brochure, Version 9, 2013).

Cabozantinib is a noncompetitive inhibitor of CYP2C8 (Kiapp = $4.6 \mu M$), a mixed-type inhibitor of both CYP2C9 (Kiapp = $10.4 \mu M$) and CYP2C19 (Kiapp = $28.8 \mu M$), and a weak competitive inhibitor of CYP3A4 (estimated Kiapp = $282 \mu M$) in HLM preparations. IC50 values >20 μM were observed for CYP1A2, CYP2D6, and CYP3A4 isozymes in both recombinant and HLM assay systems. Cabozantinib at steady-state plasma concentrations ($\geq 100 \text{ mg/day daily for a minimum of } 21 \text{ days}$) showed no effect on single-dose rosiglitazone (a CYP2C8 substrate) plasma exposure (Cmax and AUC) in patients with solid tumors (Investigator Brochure, Version 9, 2013).

Cabozantinib is an inducer of CYP1A1 mRNA in human hepatocyte incubations (i.e., 75-100% of CYP1A1 positive control β-naphthoflavone induction), but not of CYP1A2, CYP2B6, CYP2C8, CYP2C9, CYP2C19 or CYP3A4 mRNA or isozyme-associated enzyme activities (Investigator Brochure, Version 9, 2013).

Cabozantinib is an inhibitor (IC50 = $7.0 \mu M$), but not a substrate, of P-gp transport activities in a bi-directional assay system using MDCK-MDR1 cells (Investigator Brochure, Version 9, 2013).

